7.1.2.5.2 Guidelines for Evaluation of Measurable Disease

All measurements should be taken and recorded in metric notation using a ruler or physical calipers. All baseline evaluation studies should be performed as closely as possible to the beginning of treatment and never more than 4 weeks before the beginning of treatment. The same method of assessment and the same technique should be used to characterize each identified and reported lesion at baseline and during follow-up. Imaging-based evaluation is preferred to evaluation by clinical examination when both methods have been used to assess the antitumor effect of a treatment.

Clinical lesions. Clinical lesions will only be considered measurable when they are superficial (e.g., skin nodules and palpable lymph nodes). In the case of skin lesions, documentation by color photography, including a ruler to estimate the size of the lesion, is recommended.

Chest x-ray. Lesions on chest X-ray are acceptable as measurable lesions when they are clearly defined and surrounded by aerated lung. However, cross sectional imaging is preferable.

Multidetector CT, PET/CT. These techniques should be performed with contiguous slices of 5 mm or less in thickness. This applies to tumors of the neck, chest, abdomen and pelvis. Head and neck tumors and those of extremities may require specific imaging protocols or evaluation with ultrasound. When the primary endpoint of the study is objective response evaluation, US should not be used to measure tumor lesions. It is, however, a possible alternative to clinical measurements of superficial palpable lymph nodes, subcutaneous lesions, and thyroid nodules. US might also be useful to confirm the complete disappearance of superficial lesions usually assessed by clinical examination.

Endoscopy, Laparoscopy. These will not be used to assess response on this study.

Tumor markers. Tumor markers alone cannot be used to assess response. If markers are initially above the upper normal limit, they must normalize for a patient to be considered in complete clinical response.

Cytology, Histology. These techniques can be used to differentiate between partial responses (PR) and complete responses (CR) if clinically indicated.

7.1.2.5.3 Immune Related Response Criteria (irRC).

Evaluation of Target Lesions

Response in new patients will be conducted using the Immune Related Response Criteria (irRC) as described in¹⁰. “For irRC, only index and measurable new lesions are taken into account. At the baseline tumor assessment, the sum of the products of the two largest perpendicular diameters (SPD) of all index lesions (five lesions per organ, up to 10 visceral lesions and five cutaneous index lesions) is calculated. At each subsequent tumor assessment, the SPD of the index lesions and of new, measurable lesions ($\geq 5 \times 5$ mm; up to 5 new lesions per organ: 5 new cutaneous lesions and 10 visceral lesions) are added together to provide the total tumor burden:”

For the purposes of this study, 3 separate tumor burdens will be calculated for each patient and used to define 3 separate irRCs as discussed in 9.3. All criteria will be considered separately for all 3 irRCs: global, in-field, and out-field.

Global Tumor Burden = SPD(all index lesions) + SPD(new, measurable lesions)

In-Field Tumor Burden = SPD(all index lesions targeted by XRT in this protocol) + SPD(new, measurable lesions inside the XRT PTV)

Out-Field Tumor Burden = SPD(all index lesions NOT targeted by XRT in this protocol) + SPD(new, measurable lesions outside the XRT PTV)

Complete Response (irCR): irCR, complete disappearance of all lesions (whether measurable or not, and no new lesions) confirmation by a repeat, consecutive assessment no less than 4 wk from the date first documented.

Partial Response (irPR): irPR, decrease in tumor burden $\geq 50\%$ relative to baseline confirmed by a consecutive assessment at least 4 wk after first documentation.

Progressive Disease (irPD): irPD, increase in tumor burden $\geq 25\%$ relative to nadir (minimum recorded tumor burden) confirmation by a repeat, consecutive assessment no less than 4 wk from the date first documented.

1. If a patient is classified as having irPD at a post-baseline tumor assessment, then confirmation of irPD by a second scan in the absence of rapid clinical deterioration is required. The definition of confirmation of progression represents an increase in tumor burden $\geq 25\%$ compared with the nadir at two consecutive time points at least 4 wk apart. It is recommended that this be done at the discretion of the investigator

because follow-up with observation alone may not be appropriate for patients with a rapid decline in performance status.

Stable Disease (irSD): irSD, not meeting criteria for irCR or irPR, in absence of irPD. In contrast to other response criteria, this criteria does not require repeat confirmation.

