2.2 Trial Diagram

- For Part A we will allow induction chemotherapy
- Primary Endpoint
 - Safety
- Secondary endpoint
 - Improvement in PFS compared to historical controls

[figure not shown]
Part A: Is only for patients with Limited Stage SCLC, we will allow induction chemotherapy. The total cycles of chemotherapy recommended will be 4, as such if a patient had two cycles of induction chemotherapy they would only get an additional two with MK-3475. PCI will be allowed based on the treating physician discretion and will be done after chemotherapy has been completed. PCI will delay the next dose of MK-3475 by one cycle and PCI should start approximately three weeks after MK-3475. MK-3475 can be resumed following the completion of PCI. LS-SCLC patients, who achieve systemic disease control during/after completion of 16 cycles of MK-3475, will be eligible to get additional 16 cycles of MK-3475, provided they did not exhibit severe (grade >3) MK-3475 related toxicity during therapy. Systemic disease control is defined as stable disease or partial response or complete response, based on irRC criteria.

Part A for LS-SCLC

* Eligible patients may receive additional 16 cycles.

Part B: Is only for patients with Extensive Stage SCLC who are receiving consolidation XRT after 1-6 cycles of chemotherapy. Patients needing PCI are encouraged to have it completed prior to enrollment in this trial. If PCI needs to be given on study, after thoracic XRT, then it should be done in a manner consistent with part A. PCI will delay the next dose of MK-3475 by one cycle and PCI should start approximately three weeks after MK-3475. MK-3475 can be resumed following the completion of PCI.) Patients needing XRT treatment to other sites outside the thorax will be allowed, but is encouraged to be done prior to starting the trial.

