5.1.3 Subject Exclusion Criteria

The subject must be excluded from participating in the trial if the subject:

1. Is currently participating in or has participated in a study of an investigational agent (except glutamine) or using an investigational device within 2 weeks of the first dose of treatment.
2. Has a diagnosis of immunodeficiency or is receiving systemic steroid therapy or any other form of immunosuppressive therapy within 7 days prior to the first dose of trial treatment. With the exception of physiologic steroid replacement.
3. Has had a prior monoclonal antibody within 2 weeks prior to study Day 1 or who has not recovered (i.e., \leq Grade 1 or at baseline) from adverse events due to agents administered more than 4 weeks earlier.
4. Has had prior chemotherapy, targeted small molecule therapy, within 2 weeks prior to study Day 1 or who has not recovered (i.e., \leq Grade 1 or at baseline) from adverse events due to a previously administered agent. Prior radiation does not require a washout period.
 - Note: Subjects with \leq Grade 2 neuropathy are an exception to this criterion and may qualify for the study.
 - Note: If subject received major surgery, they must have recovered adequately from the toxicity and/or complications from the intervention prior to starting therapy.
5. Has a known additional malignancy that is progressing or requires active treatment. Exceptions include basal cell carcinoma of the skin, squamous cell carcinoma of the skin, or in situ cervical cancer that has undergone potentially curative therapy.
6. Has known active central nervous system (CNS) metastases and/or carcinomatous meningitis. Subjects with previously treated brain metastases may participate provided they are stable (without evidence of progression by imaging for at least four weeks prior to the first dose of trial treatment and any neurologic symptoms have returned to baseline), have no evidence of new or enlarging brain metastases, and are not using steroids for at least 7 days prior to trial treatment.

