5.4.2 Prohibited Concomitant Medications

Subjects are prohibited from receiving the following therapies during the Screening and Treatment Phase (including retreatment for post-complete response relapse) of this trial:

- Anti-cancer systemic chemotherapy or biological therapy
- Immunotherapy not specified in this protocol
- Chemotherapy not specified in this protocol
- Investigational agents other than MK-3475
- Live vaccines within 30 days prior to the first dose of trial treatment and while participating in the trial. Examples of live vaccines include, but are not limited to, the following: measles, mumps, rubella, chicken pox, yellow fever, rabies, BCG, and typhoid (oral) vaccine. Seasonal influenza vaccines for injection are generally killed virus vaccines and are allowed; however intranasal influenza vaccines (e.g. Flu-Mist®) are live attenuated vaccines, and are not allowed.

- Glucocorticoids for any purpose other than to modulate symptoms from an event of clinical interest of suspected immunologic etiology. The use of physiologic doses of corticosteroids may be approved after consultation with the Sponsor.

Subjects who, in the assessment by the investigator, require the use of any of the aforementioned treatments for clinical management should be removed from the trial. Subjects may receive other medications that the investigator deems to be medically necessary.

The Exclusion Criteria describes other medications which are prohibited in this trial.

There are no prohibited therapies during the Post-Treatment Follow-up Phase.

5.5 Correlative Studies relating to immunologic response:

The immunotherapy platform will perform immune monitoring, including but not limited to evaluation of CD4 and CD8 T cells in peripheral blood and available tumor samples as previously published, 19,22. All samples will be collected and analyzed as per a separate IRB-approved lab protocol.

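### Nothing requires the baseline scan to follow the last pre-study chemotherapy dose, so shrinkage from that cycle can count toward irPR, chiefly in Part B

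*Combined protocol and SAP*

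**What the plan says.** **Scan timing.** Section 7.1.2.5.2 requires baseline studies to be "performed as closely as possible to the beginning of treatment and never more than 4 weeks before the beginning of treatment". The flow chart in Section 6.1 puts baseline tumor imaging in a screening column that runs from Day -28 to Day -1.

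**Prior chemotherapy.** Exclusion 4 in Section 5.1.3 excludes a subject who "Has had prior chemotherapy, targeted small molecule therapy, within 2 weeks prior to study Day 1". Section 2.2 describes Part B as patients "who are receiving consolidation XRT after 1-6 cycles of chemotherapy". For the other part it says "For Part A we will allow induction chemotherapy".

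**Chemotherapy during screening.** Section 5.4.2 states "Subjects are prohibited from receiving the following therapies during the Screening and Treatment Phase", and the first item on its list is "Anti-cancer systemic chemotherapy or biological therapy".

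**Response rules.** Section 7.1.2.5.3 defines irPR as a fall in tumor burden of at least 50% "relative to baseline confirmed by a consecutive assessment at least 4 wk after first documentation". It defines irPD as a rise of at least 25% over the nadir, meaning the lowest burden recorded so far. Both apply separately to the global, in-field and out-field burdens.

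**Use of the results.** Section 9.2.4 plans Kaplan-Meier estimates and summaries with confidence intervals, and rules out formal comparison with historical controls. Section 9.1 counts every patient who receives any MK-3475 as evaluable for response.

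**The concern.** The scan may be up to 4 weeks old, and chemotherapy may continue to within 2 weeks of Day 1. A dose can therefore fall between the baseline scan and the start of study treatment. The recorded baseline is then a burden from before that dose, and whatever the dose achieves is scored as change on study.

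Part B is where this matters most. It gives MK-3475 with thoracic radiation and no concurrent chemotherapy (Sections 4.2.2 and 9.0). Shrinkage outside the radiation field would naturally be read as the systemic effect that Section 4.2.1 hopes to see, and the out-field irRC exists to capture it. Residual chemotherapy effect acts on those same lesions and would look the same.

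Progression is also touched, but less. Before any on-study scan, the only recorded nadir is the baseline itself. If that baseline is higher than the true Day 1 burden, early regrowth may not reach the irPD threshold at the first on-study scan.

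**Working it through.** **Inputs from the documents.** Maximum scan age 28 days (Sections 7.1.2.5.2 and 6.1). Minimum chemotherapy-free interval 14 days (Section 5.1.3). irPR at a 50% fall from baseline and irPD at a 25% rise from nadir (Section 7.1.2.5.3). First on-study imaging at cycle 4, then about every 12 weeks, plus or minus 4 (Section 6.1). The start of treatment and study Day 1 are taken as the same date. The plan gives no figure of its own to reproduce here.

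**Step 1, the overlap.** 28 - 14 = 14 days in which a chemotherapy dose allowed by exclusion 4 could follow a baseline scan allowed by Section 7.1.2.5.2. This counts calendar days, not patients.

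**Step 2, the thresholds.** Let *s* be the fractional fall in the sum of products of diameters (SPD) between the scan and Day 1. The documents give no value, so *s* is an assumption. Set the scanned burden to 1, so that the Day 1 burden is 1 - *s*.

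- Further fall from Day 1 needed for irPR: 1 - 0.5/(1 - *s*)
- Growth from Day 1 needed for irPD at the first scan, when the nadir is still the baseline: 1.25/(1 - *s*) - 1

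| Assumed *s* | True fall needed for irPR | True growth needed for first-scan irPD |
|---|---|---|
| 0 | 50.0% | 25.0% |
| 10% | 1 - 0.5/0.9 = 44.4% | 1.25/0.9 - 1 = 38.9% |
| 20% | 1 - 0.5/0.8 = 37.5% | 1.25/0.8 - 1 = 56.3% |
| 30% | 1 - 0.5/0.7 = 28.6% | 1.25/0.7 - 1 = 78.6% |

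**Step 3, how long irPD stays masked.** The irPR distortion persists because baseline never changes. The irPD distortion does not. With *s* = 30%, if the first on-study scan records 0.7, that becomes the nadir and irPD is called at 0.7 × 1.25 = 0.875, which is 25% above the Day 1 burden again.

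As an illustration, assume exponential regrowth from Day 1, scans at day 63 (3 cycles × 21 days) and every 84 days after that, and ignore confirmation. The table shows the scan day on which the irPD threshold is first met.

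| Assumed doubling time | *s* = 0 | *s* = 10% | *s* = 30% |
|---|---|---|---|
| 60 days | 63 | 63 | 63 |
| 120 days | 63 | 63 | 147 |
| 180 days | 63 | 147 | 147 |
| 240 days | 147 | 147 | 147 |
| 480 days | 231 | 231 | 231 |

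In these cases the delay is either nil or one imaging interval. It arises at intermediate growth rates.

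**Step 4, whether another section closes the gap.** Section 5.4.2 is the only candidate. Taken literally from Day -28, it would forbid a cycle after a screening scan. Three things stop it from settling the matter:

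- It contradicts exclusion 4, whose chemotherapy bar starts only 2 weeks before Day 1.
- Its first item has no exception for the platinum and etoposide that Part A receives on study (Section 8.0), so the list cannot be applied exactly as written.
- The start of the Screening Phase for an individual patient is not defined. If it begins later than Day -28, a standard-of-care scan and a cycle could both fall before it, and the scan could still be under 4 weeks old.

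**The case against.** The best counter-argument is Section 5.4.2. A reader might infer that a site can satisfy every rule, scan at Day -28 and then routinely give a full cycle. The documents do not support that. On a literal reading Section 5.4.2 forbids it, and Section 7.1.2.5.2 asks for the scan as near to treatment as possible, with 4 weeks only as the outer limit. Nothing shows that the sequence would be common. What stands is narrower: Sections 5.1.3, 5.4.2 and 7.1.2.5.2 do not agree on what may happen before Day 1, and none of them orders the scan and the last dose.

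A reader might also infer that irPD is delayed, and PFS lengthened, throughout follow-up. The nadir rule defeats that; the effect is mainly at the first on-study scan.

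Three further points are fair:

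- In Part A, response already mixes chemotherapy, radiation and MK-3475, so re-timing the scan cannot isolate a drug effect there.
- The direction of the bias assumes shrinkage between scan and Day 1. If tumors grow in that interval, an early scan counts against the regimen.
- Efficacy is secondary and descriptive, and neither the DLT rules nor the choice of dose uses the baseline scan. One qualification is that Section 5.8 lists confirmed radiographic progression as a reason for discontinuation, so a missed first-scan irPD is not only a matter for the tables.

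**Conclusion.** The concern holds in a limited form. The documents leave open whether the baseline scan precedes or follows the last pre-study chemotherapy dose. Where it precedes, shrinkage from that dose is credited to study treatment in irPR. The exposure is chiefly in Part B and chiefly in the out-field irRC. Masking of irPD is possible, but mainly at the first on-study scan.

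Frequency and size are unknown. The 10% to 30% range for *s* is an assumption, and the doubling times are illustrative. The 14-day overlap should not be read as half of patients being affected. The primary safety endpoint and dose escalation are unaffected. The change is still worth making, because it is cheap and the affected readout is the one meant to show a systemic effect.

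**What to change.** 1. In Section 7.1.2.5.2, and in a footnote to the imaging row of Section 6.1, state that the baseline scan must be within 4 weeks before Day 1 and after the last dose of any pre-study chemotherapy, as late in the existing washout as practicable. Record both dates.
2. Where only an earlier scan exists, keep the patient in the efficacy set, as Section 9.1 requires, and flag the patient. Report the irRC response tables with and without flagged patients as a sensitivity analysis. Dropping these patients outright would contradict Section 9.1.
3. Reconcile exclusion 4 in Section 5.1.3 with Section 5.4.2 on chemotherapy during screening. Which rule should prevail is for the investigators to decide.

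The cost is one sentence, one footnote, two recorded dates and one extra set of tables. Scan timing becomes tighter, and a few baseline scans will have to be re-timed. A scan taken soon after the last dose can still precede part of that cycle's effect, so the bias is reduced but not fully removed.

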7.1.2.6 Laboratory Safety Evaluations (Hematology, Chemistry and Urinalysis)

The total amount of blood/tissue to be drawn/collected over the course of the trial (from pre-trial to post-trial visits), including approximate blood/tissue volumes drawn/collected by visit and by sample type per subject can be found in the Procedures Manual.

Laboratory tests for screening should be performed within 28 days prior to the first dose of treatment. After Cycle 1, pre-dose laboratory procedures can be conducted up to 72 hours prior to dosing. Results must be reviewed by the investigator or qualified designee and found to be acceptable prior to each dose of trial treatment.

7.1.3 Other Procedures

7.1.3.1 Withdrawal/Discontinuation

When a subject discontinues/withdraws prior to trial completion, all applicable activities scheduled for the final trial visit should be performed at the time of discontinuation. Any adverse events which are present at the time of discontinuation/withdrawal should be followed in accordance with the safety requirements outlined in Section 7.2 - Assessing and Recording Adverse Events. Subjects who a) attain a CR or b) complete 24 months of treatment with MK-3475 may discontinue treatment with the option of restarting treatment if they meet the criteria specified. After discontinuing treatment following assessment of CR, these subjects should return to the site for a Safety Follow-up Visit (described in Section 7.1.5.3.1) and then proceed to the Follow-Up Period of the study (described in Section 7.1.4.4).

7.1.4 Visit Requirements

Visit requirements are outlined in Section 6.0 - Trial Flow Chart. Specific procedure-related details are provided above in Section 7.1 - Trial Procedures.

7.1.4.1 Screening

The screening assessment will consist of a full history and physical exam, along with listed laboratory screening tests including a pregnancy test in PT/INR.

7.1.4.2 Treatment Period

During treatment patients will have a review of all concurrent medication, vitals and review of adverse events. During radiation delivery patients will see a doctor weekly to review treatments address issues, any potential side effects.

7.1.4.3 Post-Treatment Visits

Following the completion of this study, patients will follow up one month later with new imaging studies to assess response to treatment. At this time we will also perform a physical exam, vitals, medication review, and assess for any prior and or new toxicities and or side effects. Following this the same assessment will be performed every three months for the next 2 years and then every 6 months after that.

7.1.5.3.1 Safety Follow-Up Visit

The mandatory Safety Follow-Up Visit should be conducted approximately 30 days after the last dose of trial treatment or before the initiation of a new anti-cancer treatment, whichever comes first. All AEs that occur prior to the Safety Follow-Up Visit should be recorded. Subjects with an AE of Grade > 1 will be followed until the resolution of the AE to Grade 0-1 or until the beginning of a new anti-neoplastic therapy, whichever occurs first. SAEs that occur within 90 days of the end of treatment or before initiation of a new anti-cancer treatment should also be followed and recorded.

7.1.4.4 Follow-up Visits

Subjects who discontinue trial treatment for a reason other than disease progression will move into the Follow-Up Phase and should be assessed every 12 weeks (90 ± 14 days) by radiologic imaging to monitor disease status. Every effort should be made to collect information regarding disease status until the start of new anti-neoplastic therapy, disease progression, death, end of the study. Information regarding post-study anti-neoplastic treatment will be collected if new treatment is initiated.

7.1.4.4.1 Survival Follow-up

Once a subject experiences confirmed disease progression or starts a new anti-cancer therapy, the subject moves into the survival follow-up phase and should be contacted by telephone every 12 weeks to assess for survival status until death, withdrawal of consent, or the end of the study, whichever occurs first.

7.2 Assessing and Recording Adverse Events

An adverse event is defined as any untoward medical occurrence in a patient or clinical investigation subject administered a pharmaceutical product and which does not necessarily have to have a causal relationship with this treatment. An adverse event can therefore be any unfavorable and unintended sign (including an abnormal laboratory finding, for example), symptom, or disease temporally associated with the use of a medicinal product or protocol-specified procedure, whether or not considered related to the medicinal product or protocol-specified procedure. Any worsening (i.e., any clinically significant adverse change in frequency and/or intensity) of a preexisting condition that is temporally associated with the use of the Merck's product, is also an adverse event.

Changes resulting from normal growth and development that do not vary significantly in frequency or severity from expected levels are not to be considered adverse events. Examples of this may include, but are not limited to, teething, typical crying in infants and children and onset of menses or menopause occurring at a physiologically appropriate time.

Merck product includes any pharmaceutical product, biological product, device, diagnostic agent or protocol-specified procedure, whether investigational (including placebo or active comparator medication) or marketed, manufactured by, licensed by, provided by or distributed by Merck for human use.

Adverse events may occur during the course of the use of Merck product in clinical trials or within the follow-up period specified by the protocol, or prescribed in clinical practice, from overdose (whether accidental or intentional), from abuse and from withdrawal.

Adverse events may also occur in screened subjects during any pre-allocation baseline period as a result of a protocol-specified intervention, including washout or discontinuation of usual therapy, diet, placebo treatment or a procedure.

All adverse events will be recorded from the time the consent form is signed through 30 days following cessation of treatment and at each examination on the Adverse Event case report forms/worksheets. The reporting timeframe for adverse events meeting any serious criteria is described in section 7.2.3.1.

Adverse events will not be collected for subjects during the pre-screening period (for determination of archival tissue status) as long as that subject has not undergone any protocol-specified procedure or intervention. If the subject requires a blood draw, fresh tumor biopsy etc., the subject is first required to provide consent to the main study and AEs will be captured according to guidelines for standard AE reporting.

7.2.1 Definition of an Overdose for This Protocol and Reporting of Overdose to the Sponsor and to Merck

For purposes of this trial, an overdose will be defined as any dose exceeding the prescribed dose for MK-3475 by 20% over the prescribed dose. No specific information is available on the treatment of overdose of MK-3475. In the event of overdose, MK-3475 should be discontinued and the subject should be observed closely for signs of toxicity. Appropriate supportive treatment should be provided if clinically indicated.

If an adverse event(s) is associated with (“results from”) the overdose of a Merck product, the adverse event(s) is reported as a serious adverse event, even if no other seriousness criteria are met.

If a dose of Merck’s product meeting the protocol definition of overdose is taken without any associated clinical symptoms or abnormal laboratory results, the overdose is reported as a non-serious Event of Clinical Interest (ECI), using the terminology “accidental or intentional overdose without adverse effect.”

All reports of overdose with and without an adverse event must be reported within 24 hours to the Sponsor and within 2 working days hours to Merck Global Safety. (Attn: Worldwide Product Safety; [contact])

